## **Eligibility Criteria**

When patients first register on the Active Brains study website they will answer a series of screening questions to make sure that they fit the study inclusion criteria below. Figure 1 outlines the participant identification and screening procedures.

To be eligible for inclusion, individuals with signs of cognitive decline will:

- Be aged between 60 and 85 years old inclusive
- Have cognitive impairment (AACD) defined as 1 SD below the norm on the Baddeley reasoning test [47]. A key subgroup is MCI, which will be defined simply as 1.5 SD below the norm on the Baddeley reasoning test. In statistical analysis we will also explore the impact in subgroups defined by alternative combinations of impairment in Baddeley reasoning, IADL and memory e.g. of MCI defined as 1.5SD below the norm in another non-memory cognitive domain plus memory impairment [5, 12, 13], and AACD defined as 1 SD below the norm for the Baddeley reasoning test [47] and IADL.
- Be willing and able to access the internet
- Not have an existing diagnosis of dementia at baseline
- Not report high levels of leisure time physical activity already (i.e. score 30 or more on the Godin Leisure Time Exercise Questionnaire (counting moderate or vigorous physical activity only)).
- Will not have a recorded diagnosis of long-COVID in their medical records at baseline

To be eligible for inclusion individuals without signs of cognitive decline will:

- Be aged between 60 and 85 years old inclusive
- Have normal cognitive function (i.e. do not meet criteria for cognitive impairment as defined above)
- Be willing and able to access the internet
- Not have an existing diagnosis of dementia at baseline

- Not report high levels of leisure time physical activity already (i.e. score 30 or more on the Godin Leisure Time Exercise Questionnaire (counting moderate or vigorous physical activity only)).
- Will not have a recorded diagnosis of long-COVID in their medical records at baseline

#### Randomisation

Patients will be randomised online using the study software. They will have an equal chance of being in each of the three groups in each of the two trials (the trial among those with cognitive impairment, and the trial among those with no cognitive impairment). Once randomised, participants will be informed of their group allocation (they will also be emailed this information). If participants are in one of the treatment arms they will be taken directly to Active Brains where they can begin the intervention. These participants can then use Active Brains as much as they would like to over the course of the study. The central facilitator will be notified by email when a participant is randomised to the support arm of the trial, so that they know to expect to provide support to the participant in the coming weeks.

## **Consent and Screening**

Consent will be collected online (a method we have used successfully in our PRIMIT and CLASP trials [45]). Following consent participants will complete online screening to check that they meet the above eligibility criteria for the study. Those who are ineligible based on the screening measures will receive immediate feedback which thanks them for their time, advises that they are not eligible and explains the reason for this (e.g. that they are already very highly physically active).

Should participants' scores on the online cognitive assessment screening tools meet the threshold for cognitive impairment, they will be recruited to the cognitively impaired trial.

Those whose scores do not meet the threshold for cognitive impairment will not be excluded, as we are also aiming to recruit at least 10,515 participants to a trial of Active Brains amongst those who do not show signs of cognitive decline. However, given that we may not recruit participants to the two trials at an even rate, and the fact that a slightly larger number of participants with cognitive decline are required, it is possible we will reach our recruitment target for the non-cognitively impaired trial (n= 10,515) before recruitment into the cognitively impaired trial is complete. Once we have recruited a minimum of 10,515 people to the non-cognitively impaired trial, further participants without signs of impairment will be given the

opportunity to participate in a non-randomised cohort study which will provide the same digital intervention as in the full trial, with online self-completion of follow up only (we won't do a notes review or provide additional support from a centralised facilitator to this group). Whilst we don't expect it to be the case, in the unlikely event that we reach our recruitment target for the cognitively impaired trial first (n = 10,940), any additional individuals beyond this target would enter the cohort study. This would be instead of the cohort group being populated by over-recruitment from the non-cognitively impaired trial (which we think is more likely). After initial screening indicates that these participants are eligible, and that they are not needed for the randomised trial, these participants will be shown a different participant information sheet for a cohort study online and will complete a slightly different consent form. This procedure could be beneficial for participants without signs of impairment who will get access to the Active Brains intervention and will enable us to examine how the intervention might be implemented outside of a randomised trial (which will be more similar to the effects one might expect if implementing in clinical practice).

## The Active Brains intervention

The Active Brains digital intervention provides interactive, tailored support to encourage older adults to engage in behaviours beneficial for their cognitive and physical health. The intervention content utilises behaviour change techniques to motivate users to engage in, and maintain, evidence-based activities for sustaining cognitive health in later life. All intervention content has been iteratively developed with extensive input from the target user

group to ensure that it is highly accessible and engaging. For the first seven months, users will have access to the Active Brains 'Starter Section' which provides support for users to initiate changes to their lifestyle in line with the intervention's recommendations.

#### **Active Brains Starter Section**

Within the first section of Active Brains, three primary modules will become available to users sequentially. Within these modules, users will have access to: information addressing common concerns, instruction about recommended activities, facilities to set and review goals about their chosen activities, tailored motivational feedback about their progress, and reminder emails to motivate them to continue with their activities and to revisit intervention content as appropriate. Additional detail about each of the main modules is provided below.

#### Active Lives

The 'Active Lives' module supports users in gradually increasing their levels of physical activity in a manner that is most suited to their present physical capabilities and level of activity. Within this module, there are three sub-modules that users are directed to differentially depending on which is deemed to be most beneficial for them. The 'Getting Active' sub-module provides support and ideas about activities to try to increase individuals' overall levels of physical activity. The 'Breaks from Sitting' sub-module supports individuals in reducing sedentary behaviour by suggesting simple changes that can be made to daily routines. The 'Strength and Balance Training' module provides video demonstrations of simple strength and balance exercises and suggestions about how these can be built into daily activities. The level of exercise difficulty is tailored to the user and their progress. Whilst tailored recommendations will be made about which sub-module users may find most helpful, they will have access to all three sub-modules.

## Brain Training

The Brain Training module follows on from Active Lives and is accessible to participants after four weeks. This module provides brief information about the rationale and evidence base for Brain Training tasks and how they are intended to work. The module initially provides participants with access to six online brain training games (via the existing PROTECT website) which they are encouraged to play between three and five times per week. Users are encouraged to set and review goals relating to their use of the brain training games. At regular intervals throughout the six month period of the starter session, six additional games are made available to users.

#### Eat for Health

The Eat for Health module follows on from Brain Training and becomes accessible to participants eight weeks after they first use the intervention. This module outlines the benefits of healthy eating for cognitive and physical health. It offers suggestions about specific foods and food groups that are beneficial for cognitive health. It also provides users with information and techniques to allow them to make healthy changes to their existing eating behaviours more generally (e.g. increasing fruit and vegetable consumption, cutting down on processed foods).

### **Active Brains Booster Section**

After seven months, it is expected that the primary needs of intervention users will be somewhat different. It is likely that, with support from the Active Brains Starter Sessions, the recommended activities that users have chosen to engage with will have become more habitual behaviours. These users are, therefore, expected to have less need to rely on the intervention content so extensively. Accordingly, at this stage, users will be directed to access the Active Brains Booster section. This content will include access to all content from the Starter Section, as well as advice on a 'maintenance' schedule for brain training, and centralised links to external resources for additional support and to extend their progress with the behavioural changes made.

Our previous qualitative studies (REC reference SC/17/0463), explored the acceptability of Active Brains amongst target users. Analysis of our think aloud and semi-structured interviews (n=59) informed iterative changes to the intervention content throughout development and indicated that the intervention is acceptable to older adults with and without cognitive decline. This phase also sought extensive input from PPI representatives in the development of intervention content and participant recruitment materials. Our development phase qualitative work is currently being prepared for submission for publication.

### **Central Facilitator Support**

Patients in the group receiving support from a central facilitator (in addition to the website) will be offered a brief (10 minute) telephone support call 2 weeks after they begin the study. In this support call they will discuss the cognitive/lifestyle changes that they are choosing to try. Patients will be offered two more support contacts by phone (up to 10 minutes) or email to support them in making behavioural changes. Should the participant not yet have

accessed Active Brains at the time of contact, the supporter will check whether the participant is having any technical difficulties and/or talk through any other barriers to getting started.

For patients who feel the need, up to 7 further email or phone contacts can be arranged. In the feasibility study only one participant requested additional contact beyond the three initial calls (n = 120 in support arm). In our previous studies only around 10-15% of patients have required this further support.

The central facilitator will use the CARE (Congratulate, Ask, Reassure, Encourage) approach to provide support to patients, which is based on Self-Determination Theory [52] and designed to promote autonomous motivation for making behavioural changes. The CARE approach has been used successfully in our previous trials and has been shown to be acceptable to patients and staff supporting patients [53]. Supporters will also provide brief technical website support to all participants as required throughout all contact points (e.g. advice on logging in problems). To maximise fidelity of support delivery, a 'checklist' of the CARE approach is provided in the supporter training materials that supporters are encouraged to use to guide their calls with participants. This will also include space to write notes about these interactions. As a means of fidelity check, supporters will be encouraged to share the completed checklists/notes from one or two of these anonymous interactions with the research team. A member of the research team with expertise in the CARE approach will provide feedback to the supporter as appropriate.

#### **Usual Care**

The comparison group will receive usual care from their GP practice, plus brief online advice about getting more active, improving diet and staying mentally active.

#### **Measures**

See table 2 for a full list of measures at each time point, for each study group.

Participants in both the randomised trials and cohort study will be followed-up every 12 months for the five year duration of the study. At years one and five, participants will be asked to complete a full set of follow-up measures. In years two, three and four participants will only be requested to complete a subset comprising the most important outcome measures. At the start of each follow-up time point, participants will receive three automated email reminders to complete follow-up measures, at one week intervals (cancelled if they complete the measures in the meantime). In follow-up years two, three and four, after this point we will not contact participants about completing measures any further. At years one

and five, if participants in the randomised trial (not cohort participants) do not complete follow-up measures after the three email reminders then we will contact them by post with a brief letter explaining the importance of completing measures online with instructions about how to login. If this is unsuccessful, we will subsequently contact them by phone to ask them to complete the most important outcome measures (reasoning [47], Instrumental Activities of Daily Living [54], quality of life with the EQ-5D [55]). The Baddeley verbal reasoning task can only be completed online, so if phone calls are required then they will be used to prompt/support (as required) the participant to complete this task online or to ascertain that the participant is no longer able to complete these measures. If the phone call is unsuccessful, a paper version of the measures that can be completed offline will be posted with a freepost return envelope. All of the participants will be contacted to complete follow-up measures, whether or not they have used the website. If the participant indicates that they would not be willing to complete any further measures at any point then no further contact will be made regarding the follow-ups.

To maximise outcome data, participants will have the option to nominate a contact person (a friend, relative, neighbour or colleague) at sign-up. The contact person will only be contacted by the research team if the participant does not complete the follow-up measures at the one and five year follow-up points (after all procedures to reach the participant have been tried: 3 emails, 1 postal contact, provision of paper questionnaires and 1 phone call). If a participant nominates a contact person, the nominated contact person will receive an email with a link to the Active Brains website where they will be able to read a participant information sheet explaining about the study and their potential role. If they decide to act as a contact person in this study they will give consent and provide their contact details (name, email address and telephone number). Should the contact person be needed at follow-up, they will either be asked to help put the research team in touch with the participant or to complete three short questionnaires about the participant (EQ5D5L-Proxy version 2, IADL proxy version, Informant Questionnaire on Cognitive Decline in the Elderly (IQCODE) [56]).

Assuming progression to long term (5 year) follow-up, we will email participants who complete at least up to the self-report IQCODE questions within their 5 year follow-up, to ask if they would be willing for their existing contact person (if already nominated) or a new contact person of their choosing (if not nominated, or if the existing contact no longer suitable) could be contacted to complete the informant IQCODE questionnaire. This is to provide data to validate the self-report IQCODE as part of the sensitivity analysis for determination of the dementia outcome at five years. In this request, we will make it clear (in plain English language) that this is only for the purposes of answering a research question about the way the IQCODE questionnaire can be used, and would only happen with their

permission. If the participant is not happy for this to happen, no further action will be taken and no further requests would be made. If participants are happy to proceed, they will be asked to provide the name and contact details of an appropriate contact person, or to confirm that the existing one can be contacted. The contact person will then be emailed a participant information sheet, study team contact details, and a link to an online consent form to allow them to provide informed consent to provide the requested data. Should they consent by completing the online form, they will immediately be able to complete the informant IQCODE online. The contact person's name and contact details will not be available to, or saved, by the research team until after the point they have consented. If the contact person consents but does not complete the online IQCODE questionnaire, they will be sent one email prompt one week after the first request. After this, no further follow-up attempts will be made.

## Statistical analysis

Intention to treat (ITT) analysis will be performed. If the assumptions for linear modelling are met, linear regression will be used to model the primary outcome and continuous secondary outcomes. If linear modelling assumptions are not met, another appropriate parametric distribution will be sought and a suitable regression model fitted. If no suitable parametric distribution fits the data, a non-parametric approach using quantile regression will be used.

Binary outcomes will be modelled using logistic regression and count outcomes with an appropriate distribution.

All regression models will control for baseline values. The estimates for the overall trial intervention cohorts compared with the control group will be provided with 95% confidence intervals.

Depending on the patterns of missing data, it is likely that we will be using multiple imputation methods for all outcome values that are missing at follow-up, using a chained equations approach to multiple imputation based on baseline data and any available follow up data from other time points. However, we will also include sensitivity analyses - where instead of allowing the model to predict the value of the outcome measure, we set it to a value representing either poor outcome or good outcome. We will also present a sensitivity analysis using complete cases only.

The study will be reported in accordance with the CONSORT (Consolidated Standards of Reporting Trials) statement. The primary analysis will analyse the two trials separately. We

will then explore as a secondary analysis whether both trial datasets can be combined for modelling, particularly for any pre-planned subgroup analyses.

# Health economic analysis

The economic evaluation will be taken from an NHS and PSS perspective with a sensitivity analysis from a societal perspective taking employment status into account. The outcome will be expressed as incremental cost per improvement in cognitive functioning scores and per quality adjusted life year gained.

Personal out-of-pocket spending and informal care information will be collected through online questionnaires. We will record all resources required for interventions including staff support time, time using the internet, and the cost of maintaining the LifeGuide platform. Use of relevant primary/secondary care services will be extracted by notes review at years 1 and 5 of the trial. Health-related quality of life (HRQoL) questionnaires will be completed at baseline, and annually from year 1 to year 5. Personal resource usage questionnaires will be completed at years 1 and 5. All relevant resource items identified will be costed using appropriate local or national cost data (e.g. PSSRU, 2007), with informal care costed at the minimum wage level, NHS reference costs, and from participating Trusts where necessary.

EQ5D will be translated to utility score using the UK tariff. Area under the curve approach will be adopted to calculate quality adjust life years (QALYs) and discounted beyond one year for each individual.

We will follow the intention to treat principle. Generalised linear mixed models will be used to estimate the costs and QALYs difference by adjusting baseline characteristics including socioeconomic groups. Where appropriate we will estimate incremental cost-effectiveness ratios. We will estimate mean values and 95% percentiles using non-parametric bootstrapping, and use these to estimate cost-effectiveness acceptability curves. Major assumptions in the costing and analysis will be tested through sensitivity analyses. Missing value will be explored using multiple imputation and presented as sensitivity analyses.

A population dynamic model will be developed to consider prevalence, new incidence, and progression of cognitive impairment, using values informed by our literature review, data collected at feasibility stage and full trial results. We will extrapolate the trial findings to broader settings and test the cost effectiveness implications regarding different take-up rates, intensity of use, and socioeconomic variables.

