## **Primary Research Objective:**

Amongst older adults (60-85 years) both with and without cognitive impairment, the primary research objectives are:

- to estimate the effectiveness and cost-effectiveness of the Active Brains digital intervention (compared with usual care) in maintaining cognitive functioning (assessed by verbal reasoning performance).
- 2) to estimate the effectiveness and cost-effectiveness of the Active Brains digital intervention (compared with usual care) in maintaining cognitive functioning (assessed by verbal reasoning performance) when supported as necessary by a trained behavioural facilitator.

The primary outcome (effectiveness) measure at one year is an online version of the Baddeley Verbal Reasoning task.

At the five year follow-up point\*, a further primary objective is to estimate the effectiveness of the Active Brains digital intervention in delaying dementia. This will be determined in the following way:

1. If there is a notes diagnosis of dementia participants will be classed as having dementia.

As recording in notes is often sub-optimal, as sensitivity analyses, we will use the following methods to ascertain the dementia outcome:

- 2. Self-report item "Has a doctor or other medical worker ever said that you have dementia?" (Y/N) as collected in baseline and year 1 and year 5 follow-up online/paper measures.
- 3. Evidence of significant decline in Baddeley (baseline to follow-up) **AND** evidence of functional deterioration (EITHER: a) significant change in self-report IQCODE (baseline to

follow-up) OR b) two self-report questions on difficulty in finance and planning\*. These items are collected in year 5 online/paper measures.

\* The items are:

Thinking about how you were ten years ago, how are you at:

- a) handling your personal finances (banking, pension, etc)?
- b) thinking about future events and planning ahead?

(Much improved/ A bit improved/ Not much change/ A bit worse/ Much worse)

Self-completed IQCODE will be used as it is likely to provide the most complete data. However, we will also explore the agreement between self-completed IQCODE and informant completed IQCODE among willing contacts (where provided), how these relate to other outcomes, and the implications of using self-completed or informant completed measures.

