## 3.3.2 Missing data

Multiple imputation with chained equations will be used for the primary outcome and will be implemented in the mice package in Stata. The imputation model will include all variables in the analysis model and auxiliary variables, which predict the outcome or the missingness of the outcome. Predictors of the outcome or its missingness will be ascertained using LASSO regression [35]. Further details are provided in section 4.4. However, we will also include sensitivity analyses using delta-based multiple imputation, to explore the impact of a better or worse outcome for the missing values than those imputed under MAR. We will also present a sensitivity analysis using complete cases only.

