#### 4.4 Primary endpoint

The Baddeley verbal reasoning score at 1 year will be analysed using linear regression, adjusting for baseline Baddeley verbal reasoning score and age, gender, IMD score, number of comorbidities and polypharmacy (yes/no). Adjustment for prognostic covariates, specified a priori, is now commonly recommended in the primary analysis of trial data and can potentially increase power [36, 37]. Assumptions for linear regression will be checked using QQ plots for normality and residual vs fitted value plots for linearity and homoscedasticity. If linear modelling assumptions are not met, the data will be transformed using, e.g., a Box Cox transformation and back transformed at values of interest.

The primary analysis will use multiple imputation with chained equations. The imputation model will include all variables in the analysis model and any baseline covariates predictive of

the Baddeley verbal reasoning score or its missingness. Predictors of missingness will be ascertained using Lasso regression [35]. Potential auxiliary variables will include all baseline variables. A model for outcome that includes randomised group, baseline outcome and all potential auxiliary variables will be fitted using the LASSO with 10-fold cross-validation [38]. The regularization penalty (denoted by  $\lambda$ ) will be chosen such that the cross-validation error was within one SE of the minimum [39]. The auxiliary variables that are included in the fitted model from the LASSO will be included in the imputation model for the outcome, i.e., the LASSO will used to select variables for the imputation model but not to estimate parameters of the imputation model. One hundred imputations will be performed and the imputed estimates will be combined using Rubin's rules. Imputation will be performed separately by randomised group and then combined [40].

All tests will be two-tailed with point estimates and 95% confidence intervals for the treatment effect presented. No formal adjustment for multiple significance testing will be applied. Analyses will be performed using Stata version 17 or above.

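### The protocol gives multiple imputation only a sensitivity role in the economic analysis and states no other missing-data rule, so the cost-effectiveness base case appears to rest on complete data, the reverse of the clinical primary analysis

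*Protocol*

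**What the plan says.** Both primary objectives in the Protocol include cost-effectiveness; the first is "to estimate the effectiveness and cost-effectiveness of the Active Brains digital intervention (compared with usual care) in maintaining cognitive functioning". The SAP repeats this in section 1.3.

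The Protocol's Health economic analysis section contains four relevant statements:

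- Outcome: "The outcome will be expressed as incremental cost per improvement in cognitive functioning scores and per quality adjusted life year gained".
- Principle: "We will follow the intention to treat principle".
- Model: "Generalised linear mixed models will be used to estimate the costs and QALYs difference by adjusting baseline characteristics including socioeconomic groups".
- Missing data: "Missing value will be explored using multiple imputation and presented as sensitivity analyses".

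The section derives QALYs for each individual by area under the curve, from EQ-5D at baseline and at each of years 1 to 5. NHS resource use comes from notes review. No other rule for incomplete economic data is given.

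The clinical plan is ordered the other way. SAP 3.3.2 states: "Multiple imputation with chained equations will be used for the primary outcome". SAP 4.4 states: "The primary analysis will use multiple imputation with chained equations", with 100 imputations carried out separately by arm. Complete cases are a sensitivity analysis. The Protocol's Statistical analysis section goes wider and expects imputation to be likely for every outcome value missing at follow-up.

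Collection effort differs by year. At years 1 and 5 the email reminders are followed by post, phone, a paper form and, if needed, a nominated contact. In the middle years there are three emails: "In follow-up years two, three and four, after this point we will not contact participants about completing measures any further".

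**The concern.** If imputation is only a sensitivity analysis and a QALY total is formed for each person before modelling, someone missing a required EQ-5D has no QALY to model unless another rule applies. None is stated. The natural reading is a base case without imputation, and three things follow.

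- The economic result would follow the opposite missing-data hierarchy from the clinical result, although both serve the same primary objectives.
- Cost per improvement in cognitive score would use an effect estimated on a different analysed set from the imputed clinical estimate of the same score. A reader would meet two estimates of the primary outcome.
- Costs and QALYs go missing for different reasons. Notes review can supply NHS costs for people who never return an EQ-5D. Restricting to people with both discards known costs; modelling each on its own available set draws the two parts of the ratio from different people.

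The stated intention-to-treat principle fits poorly with an unimputed base case when the plan itself expects losses of 30% to 40%.

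**Working it through.** **Inputs.** Planned follow-up is 70% at year 1 and 60% at five years (Protocol, Sample Size Calculations). The recruitment targets are 10,940 (cognitive decline trial) and 10,515 (non-cognitive decline trial). These percentages were set for the Baddeley and dementia outcomes; the documents give no completion rate for EQ-5D.

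**Reproducing the plan's own totals** (required number divided by the proportion followed up):

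- Baddeley, cognitive decline: 6 × 698 / 0.7 = 5,983; 6 × 698 / 0.6 = 6,980.
- Dementia, cognitive decline: 6 × 1,094 / 0.6 = 10,940.
- Baddeley, non-cognitive decline: 3 × 2,103 / 0.7 = 9,013; 3 × 2,103 / 0.6 = 10,515.

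All agree with the Protocol, so 70% and 60% are the retention figures behind the design.

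**Year 1.** A one-year QALY needs EQ-5D at baseline and year 1 only. If EQ-5D followed the 70% planning figure, 0.7 × 10,940 = 7,658 and 0.7 × 10,515 ≈ 7,361 would have a year 1 value. If costs were also available for 90%, independently (an assumption), the share with both would be 0.7 × 0.9 = 63%.

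**Five years.** The area under the curve draws on five follow-up EQ-5Ds. The share of participants with all five depends on how missing waves cluster within people:

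| Response per wave (assumed) | Waves independent | Fully nested |
|---|---|---|
| 60% at every wave | 0.6^5 = 7.8% | 60% |
| 70% at every wave | 0.7^5 = 16.8% | 70% |
| Falling evenly from 70% to 60% | 0.70 × 0.675 × 0.65 × 0.625 × 0.60 = 11.5% | 60% |
| 70% at year 1, 40% in years 2-4, 60% at year 5 | 0.7 × 0.4^3 × 0.6 = 2.7% | 40% |

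In the third row, 11.5% is about 1,260 of 10,940 and 1,211 of 10,515; the nested 60% is 6,564 and 6,309. The same people are asked each year, so complete independence is implausible and the truth probably lies between the two columns. The last row shows how far weaker response in the email-only years would lower the share.

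**Side by side.** The clinical primary analysis has imputation primary and complete cases as sensitivity. The economic analysis has imputation as sensitivity and an unnamed base case. The Protocol's Statistical analysis section expects imputation for missing outcome values generally, and EQ-5D is an outcome; the next section makes imputation of data built on the same EQ-5D scores a sensitivity analysis. The two sections need reconciling.

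**The case against.** The strongest reply is that the Protocol never uses the term complete case for the economic analysis. It names mixed models, which could use partly observed repeated data if specified that way, and the base-case rule may be set in the health economic analysis plan, which SAP 4.6.3 places in a separate document. Imputed results will be presented in any event. This stands in part: the complete-data base case is an inference, and the separate plan might settle it. But the modelled quantity is a QALY already totalled for each person, so a mixed model would not by itself rescue someone with a missing wave. The Protocol also does more than leave a gap, because it assigns imputation to sensitivity.

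Other limits also stand:

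- A reader might infer that at least 30% are excluded at year 1. That is not a floor. The 70% is a planning figure for outcomes including the Baddeley, which can only be done online, whereas EQ-5D at years 1 and 5 can also come by phone, on paper or by proxy.
- SAP 3.3.2 prescribes imputation for the primary outcome only, and SAP 4.5.7 analyses EQ-5D by linear regression without mentioning it. The contrast is therefore between two analyses serving the same primary objectives, not between two stated rules for EQ-5D.
- Five-year follow-up is contingent on the one-year results.

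**Conclusion.** The concern holds in limited form. The Protocol gives imputation only a sensitivity role, states no alternative, and so appears to leave the economic base case to participants with complete data. This reverses the clinical ordering without a reason and is in tension with the Protocol's own Statistical analysis section and its intention-to-treat statement.

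On size, the planning figures imply about 30% missing at year 1 and 40% at year 5, with EQ-5D possibly more complete at those visits. For five-year QALYs, 60-70% response per wave gives between 8-17% (independent) and 60-70% (nested) with all five follow-up values. Both the response rate and the dependence between waves are assumptions.

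Two stronger readings are not supported. One is that the economic result will rest on a small subset: about 70% at year 1 is selected but not small, and a small share arises at five years only under weak or largely independent response. The other is that it concerns a different population or will contradict the clinical finding: both analyses state intention to treat, so what may differ is the analysed set, and neither the direction nor the size of bias can be derived from the documents.

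**What to change.** Amend the missing-data sentence in the Protocol's Health economic analysis section so that multiple imputation is the base case. Impute separately by arm and jointly over costs (including resource use from notes review), EQ-5D at each wave and baseline covariates. Form QALYs after imputation, and state how imputation is combined with the bootstrap. Present complete cases and a not-at-random scenario as sensitivity analyses. If a different base case is intended, name it and justify the departure from the clinical approach. Carry the same rule into the separate health economic analysis plan, and reconcile it with the Protocol's Statistical analysis section.

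The cost is a short protocol amendment and more computing, mainly from combining imputation with the bootstrap. The base case would then rely on a missing-at-random model, as the clinical primary analysis already does; the not-at-random scenario shows how much depends on it.
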